### 10.1.3 SAEs

An SAE is defined as any untoward medical occurrence that at any dose:

1. Results in DEATH.
2. Is LIFE THREATENING.
  - The term "life threatening" refers to an event in which the subject was at risk of death at the time of the event; it does not refer to an event that hypothetically might have caused death if it were more severe.
3. Requires inpatient HOSPITALIZATION or prolongation of existing hospitalization.
4. Results in persistent or significant DISABILITY/INCAPACITY.
5. Is a CONGENITAL ANOMALY/BIRTH DEFECT.
6. Is an IMPORTANT MEDICAL EVENT that satisfies any of the following:
  - May require intervention to prevent items 1 through 5 above.
  - May expose the subject to danger, even though the event is not immediately life threatening or fatal or does not result in hospitalization.
  - Includes any event or synonym described in the Takeda Medically Significant AE List ([Table 10.a](#)).

**Table 10.a Takeda Medically Significant AE List**

	Term
Acute respiratory failure/acute respiratory distress syndrome	Hepatic necrosis
Torsade de pointes/ventricular fibrillation/ventricular tachycardia	Acute liver failure Anaphylactic shock
Malignant hypertension	Acute renal failure
Convulsive seizure	Pulmonary hypertension
Agranulocytosis	Pulmonary fibrosis
Aplastic anemia	Confirmed or suspected endotoxin shock
Toxic epidermal necrolysis/Stevens-Johnson syndrome	Confirmed or suspected transmission of infectious agent by a medicinal product Neuroleptic malignant syndrome/malignant hyperthermia Spontaneous abortion/stillbirth and fetal death

Note: Terms identified on the Medically Significant AE List represent the broad medical concepts to be considered as “Important Medical Events” satisfying SAE reporting requirements.

#### **10.1.4 Intensity of AEs**

The different categories of intensity (severity) are characterized as follows:

- Mild: The event is transient and easily tolerated by the subject.  
Moderate: The event causes the subject discomfort and interrupts the subject’s usual activities.  
Severe: The event causes considerable interference with the subject’s usual activities.

#### **10.1.5 Causality of AEs**

The relationship of each AE to study drug will be assessed using the following categories:

- Related: An AE that follows a reasonable temporal sequence from administration of a drug (including the course after withdrawal of the drug), or for which possible involvement of the drug cannot be ruled out, although factors other than the drug, such as underlying diseases, complications, concomitant medications, and concurrent treatments, may also be responsible.  
Not Related: An AE that does not follow a reasonable temporal sequence from administration of a drug and/or that can reasonably be explained by other factors, such as underlying diseases, complications, concomitant medications, and concurrent treatments.

#### **10.1.6 Relationship to Study Procedures**

Relationship (causality) to study procedures should be determined for all AEs.

The relationship should be assessed as Related if the investigator considers that there is reasonable possibility that an event is due to a study procedure. Otherwise, the relationship should be assessed as Not Related.

### 10.1.7 Start Date

The start date of the AE is the date that the first signs/symptoms were noted by the subject and/or investigator.

### 10.1.8 Stop Date

The stop date of the AE is the date at which the subject recovered, the event resolved but with sequelae, or the subject died.

### 10.1.9 Frequency

Episodic AEs (eg, vomiting) or those which occur repeatedly over a period of consecutive days are intermittent. All other events either occur once or are continuous.

### 10.1.10 Action Concerning Study Drug

- Drug Withdrawn – a study drug is stopped due to the particular AE.
- Dose Not Changed – the particular AE did not require stopping a study drug.
- Unknown – only to be used if it has not been possible to determine what action has been taken.
- Not Applicable – a study drug was stopped for a reason other than the particular AE, eg, the study has been terminated, the subject died, or dosing with study drug was already stopped before the onset of the AE.
- Dose Reduced – the dose was reduced due to the particular AE.
- Dose Interrupted – the dose was interrupted due to the particular AE.
- Dose Increased – the dose was increased due to the particular AE.

### 10.1.11 Outcome

- Recovered/Resolved – Subject returned to first assessment status with respect to the AE.
- Recovering/Resolving – the intensity is lowered by 1 or more stages: the diagnosis or signs/symptoms has almost disappeared; the abnormal laboratory value improved, but has not returned to the normal range or to Baseline; the subject died from a cause other than the particular AE with the condition remaining “recovering/resolving”.
- Not Recovered/Not Resolved – there is no change in the diagnosis or signs/symptoms; the intensity of the diagnosis, signs/symptoms, or laboratory value on the last day of the observed study period has got worse than when it started; is an irreversible congenital anomaly; the subject died from another cause with the particular AE state remaining “not recovered/not resolved”.

- Resolved with Sequelae – the subject recovered from an acute AE but was left with permanent/significant impairment (eg, recovered from a cardiovascular accident but with some persisting paresis).
- Fatal – the AEs which are considered as the cause of death.
- Unknown – the course of the AE cannot be followed up due to hospital change or residence change at the end of the subject’s participation in the study.

## 10.2 Procedures

### 10.2.1 Collection and Reporting of AEs

#### 10.2.1.1 AE Collection Period

Collection of AEs will commence from the time informed consent is provided at Screening (Visit 1) and continue until screen failure or until the Follow-up Visit (Visit 9). For subjects who discontinue prior to study drug administration, AEs are collected until the subject discontinues study participation.

#### 10.2.1.2 AE Reporting

At each study visit, the investigator will assess whether any subjective AEs have occurred. A neutral question, such as “How have you been feeling since your last visit?” may be asked. Subjects may report AEs occurring at any other time during the study.

All subjects experiencing AEs, whether considered associated with the use of the study drug or not, must be monitored until the symptoms subside and any clinically relevant changes in laboratory values have returned to Baseline or until there is a satisfactory explanation for the changes observed. All AEs will be documented in the AE page of the eCRF, whether or not the investigator concludes that the event is related to the drug treatment. The following information will be documented for each event:

1. Event term.
2. Start and stop date and time.
3. Frequency.
4. Intensity.
5. Investigator’s opinion of the causal relationship between the event and administration of study drug (related or not related).
6. Investigator’s opinion of the causal relationship to study procedure(s), including the details of the suspected procedure.
7. Action concerning study drug.
8. Outcome of event.

## 9. Seriousness.

The seizure diary will not be used as a primary means to collect AEs. However, should the investigator become aware of a potential AE through the information recorded in the diary, proper follow-up with the subject for medical evaluation should be undertaken. Through this follow-up, if it is determined that an AE not previously reported has been identified, normal reporting requirements should be applied (see Section 10.1.2).

### 10.2.2 Collection and Reporting of SAEs

When an SAE occurs through the AE collection period it should be reported according to the following procedure:

An SAE should be completed in EDC with all mandatory information. If EDC is not available, a Takeda SAE form must be completed, in English, and signed by the investigator immediately or within 24 hours of first onset or notification of the event. The information should be completed as fully as possible but contain, at a minimum:

- A short description of the event and the reason why the event is categorized as serious.
- Subject ID number.
- Investigator's name.
- Name of the study drug.
- Causality assessment.

The SAE form should be transmitted within 24 hours to the attention of the contact listed in Section 1.1.

Any SAE spontaneously reported to the investigator following the AE collection period should be reported to the sponsor if considered related to study participation.

### 10.2.3 Reporting of Abnormal LFTs

If a subject is noted to have ALT or AST elevated  $>3 \times \text{ULN}$  on 2 consecutive occasions, as specified in Section 9.1.11, the abnormality should be recorded as an AE.

If a subject is noted to have ALT or AST  $>3 \times \text{ULN}$  and total bilirubin  $>2 \times \text{ULN}$  for which an alternative etiology has not been identified, the event should be recorded as an SAE and reported as per Section 10.2.2. The investigator must contact the Medical Monitor for discussion of the relevant subject details and possible alternative etiologies, such as acute viral hepatitis A or B or other acute liver disease or medical history/concurrent medical conditions. Follow-up laboratory tests as described in Section 9.1.11 must also be performed. In addition, relevant eCRFs must be completed and transmitted with the Takeda SAE form (as per Section 10.2.2).

### **10.3 Follow-up of SAEs**

If information not available at the time of the first report becomes available at a later date, the investigator should complete the follow-up information with additions or changes to the SAE in EDC. A paper SAE form should only be used if EDC is not available. Paper SAE forms or other written documentation should be faxed immediately within 24 hours of receipt to the attention of the contact listed in Section 1.1. Copies of any relevant data from the hospital notes (eg, ECGs, laboratory tests, discharge summary, postmortem results) should be sent to the addressee, if requested.

All SAEs should be followed up until resolution or permanent outcome of the event. The timelines and procedure for follow-up reports are the same as those for the initial report.

#### **10.3.1 Safety Reporting to Investigators, IRBs or Independent Ethics Committee, and Regulatory Authorities**

The sponsor will be responsible for reporting all suspected unexpected serious adverse reactions (SUSARs) and any other applicable SAEs to regulatory authorities, including the European Medicines Agency, investigators, and IRBs or Independent Ethics Committees (IECs), as applicable, in accordance with national regulations in the countries where the study is conducted. Relative to the first awareness of the event by/or further provision to the sponsor or sponsor's designee, SUSARs will be submitted to the regulatory authorities as expedited reports within 7 days for fatal and life-threatening events and 15 days for other serious events, unless otherwise required by national regulations. The sponsor will also prepare an expedited report for other safety issues where these might materially alter the current benefit-risk assessment of a study drug/sponsor supplied drug or that would be sufficient to consider changes in the study drug/sponsor supplied drug administration or in the overall conduct of the study. The study site also will forward a copy of all expedited reports to his or her IRB or IEC in accordance with local regulations.

## **11.0 STUDY-SPECIFIC COMMITTEES**

No steering committee, data safety monitoring committee, or clinical endpoint committee will be used in this study.

## 12.0 DATA HANDLING AND RECORDKEEPING

The full details of procedures for data handling will be documented in the Data Management Plan. AEs, medical history, and concurrent medical conditions will be coded using the Medical Dictionary for Regulatory Activities (MedDRA). Drugs will be coded using the World Health Organization Drug Dictionary.

### 12.1 eCRFs

Completed eCRFs are required for each subject who signs an informed consent form.

The sponsor or its designee will supply study sites with access to eCRFs. The sponsor will make arrangements to train appropriate site staff in the use of the eCRF. These forms are used to transmit the information collected in the performance of this study to the sponsor and regulatory authorities. eCRFs must be completed in English. Data are transcribed directly onto eCRFs.

After completion of the entry process, computer logic checks will be run to identify items, such as inconsistent dates, missing data, and questionable values. Queries may be issued by Takeda personnel (or designees) and will be answered by the site.

The principal investigator must review the eCRFs for completeness and accuracy and must e-sign the appropriate eCRFs as indicated. Furthermore, the investigator must retain full responsibility for the accuracy and authenticity of all data entered on the eCRFs.

After submission of the eCRFs to the sponsor, any change of, modification of, or addition to the data on eCRFs should be made by the investigator with use of change and modification records of eCRFs (Data Clarification Form) provided by the sponsor. The principal investigator must review the Data Clarification Form for completeness and accuracy, and must sign and date the form.

After the lock of the study database, any change of, modification of, or addition to the data on the eCRFs should be made by the investigator with the approval from the sponsor. The principal investigator must review the data change for completeness and accuracy, and must sign and date.

eCRFs will be reviewed for completeness and acceptability at the study site during periodic visits by the sponsor or its designee. The sponsor or its designee will be permitted to review the subject's medical and hospital records pertinent to the study to ensure accuracy of the eCRFs. The completed eCRFs are the sole property of the sponsor and should not be made available in any form to third parties, except for authorized representatives of appropriate governmental health or regulatory authorities, without written permission of the sponsor.

### 12.2 Record Retention

The investigator agrees to keep the records stipulated in Section 12.1 and those documents that include (but are not limited to) the study-specific documents, the identification log of all participating subjects, medical records, temporary media such as thermal sensitive paper, source worksheets, all original signed and dated informed consent forms, subject authorization forms regarding the use of personal health information (if separate from the informed consent forms), electronic copy of eCRFs, including the audit trail, and detailed records of drug disposition to

enable evaluations or audits from regulatory authorities, the sponsor, or its designees. Any source documentation printed on degradable thermal sensitive paper should be photocopied by the site and filed with the original in the subject's chart to ensure long term legibility. Furthermore, International Council for Harmonisation (ICH) E6 Section 4.9.5 requires the investigator to retain essential documents specified in ICH E6 (Section 8) until at least 2 years after the last approval of a marketing application for a specified drug indication being investigated or, if an application is not approved, until at least 2 years after the investigation is discontinued and regulatory authorities are notified. In addition, ICH E6 Section 4.9.5 states that the study records should be retained until an amount of time specified by applicable regulatory requirements or for a time specified in the study site agreement between the investigator and sponsor.

Refer to the study site agreement for the sponsor's requirements on record retention. The investigator should contact and receive written approval from the sponsor before disposing of any such documents.

The investigator and the head of the study site are required to retain essential relevant documents until the day specified as (1) or (2) below, whichever comes later. However, if the sponsor requests a longer time period for retention, the head of the study site should discuss how long and how to retain those documents with the sponsor.

1. The day on which marketing approval of the study drug is obtained (or the day 3 years after the date of notification in the case that the investigation is discontinued.)
2. The day 3 years after the date of early termination or completion of the study.

In addition, the investigator and the head of the study site should retain the essential relevant documents until the receipt of a sponsor-issued notification to state the retention is no longer required.

## 13.0 STATISTICAL METHODS

### 13.1 Statistical and Analytical Plans

A statistical analysis plan (SAP) will be prepared and finalized before database lock. This document will provide further details regarding the definition of analysis variables and analysis methodology to address all study objectives.

A blinded data review will be conducted before database lock. This review will assess the accuracy and completeness of the study database, subject evaluability, and appropriateness of the planned statistical methods.

#### 13.1.1 Analysis Sets

The randomized set will include all subjects who were randomly assigned to treatment through the IVRS/IWRS.

The PK analysis set for Parts 1 and 2 will include all subjects who received at least 1 dose of study drug and have at least 1 measurable TAK-935 or M-I plasma concentration.

CCI

The full analysis set (FAS) for Parts 1 and 2 will include all subjects who were randomized, received at least 1 dose of study drug, and have at least 1 valid postbaseline value for assessment of the efficacy endpoint(s). In FAS efficacy summaries, subjects will be analyzed according to the treatment to which they were randomized. To adjust for treatment noncompliance or insufficient treatment exposure, one or more modified FAS populations may be defined in the SAP.

The per-protocol set (PPS) for Parts 1 and 2 will include all subjects in the FAS who had no major protocol violations. Subjects to be excluded from the PPS, whether due to protocol violations or noncompliance to the dosing schedule, will be identified via a subject evaluability assessment performed before unblinding.

The safety analysis set for Parts 1 and 2 will include all subjects who received at least 1 dose of study drug. In safety summaries, subjects will be analyzed according to the treatment they received.

#### 13.1.2 Analysis of Demographics and Other Baseline Characteristics

Demographic and other baseline characteristics will be summarized and listed for enrolled subjects by treatment group and overall. Descriptive statistics will be used to summarize data for continuous variables such as age and weight (eg, number of subjects, mean, median, SD, and range) and for categorical variables such as sex, ethnicity, and race (number and percentage of subjects within each category). Medical history and medication history will be listed by subject.

### 13.1.3 Safety Analysis

#### 13.1.3.1 AEs

AEs will be reported throughout the study. TEAEs will be a primary endpoint for each part of the study. TEAEs will be summarized using descriptive statistics (number and percentage of subjects) for the safety analysis set. No statistical testing will be performed or inferential statistics will be generated.

The definition of TEAEs will be provided in the SAP. AEs will be coded using MedDRA and will be summarized by system organ class and preferred term and by treatment group separately for each part of the study.

AEs that were reported more than once by a subject during a part of the study will be counted only once for that subject at the maximum severity.

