On Day 31 (Visit 5), PK, PD, AED, and PGx (if collected on Day 1) blood samples will be collected before the morning dose of study drug and seizure data will also be collected. On Day 41 (Visit 6), PK, PD, and AED blood samples will be collected before the morning dose of study drug and seizure data will also be collected.

On Day 85 (Visit 7), subjects will return to the clinic for the Final Visit and enter the 3- or 6-day de-escalation phase. At this visit, PK, PD, and AED blood samples will be collected before the morning dose of study drug and seizure data will also be collected. Subjects will then enter the dose de-escalation phase and will be instructed to follow the applicable de-escalation dosing schedule outlined below:

- For subjects on 300 mg BID during the maintenance phase, the dose will be de-escalated to 200 mg BID for 3 days (Days 85-87) and subsequently to 100 mg BID for 3 days (Days 88-90).
- For subjects on 200 mg BID during the maintenance phase, the dose will be de-escalated to 100 mg BID for 3 days (Days 85-87).
- For subjects on 100 mg BID during the maintenance phase, there is no de-escalation and the dose is discontinued on Day 85.

Immediately after the last dose is the 30-day Follow-up Period comprised of a Follow-up Phone Call (Visit 8) on Day 91 and a Follow-up Visit (Visit 9) on Day 121. At the Follow-up Visit, subjects will return to the clinic for study procedures including PD and AED blood sample collection.

In Parts 1 and 2, subjects will be instructed to not take their morning dose of study drug or concomitant AEDs on the days of scheduled study visits to facilitate collection of the predose PK, PD, AED, and optional PGx blood samples. The morning dose of study drug and concomitant AEDs will be administered in the clinic on these study days after laboratory samples are collected. For subjects who are not able to come for the visit during the morning hours, they should be instructed to take their morning dose, as usual, and come to the study site during the afternoon hours, as feasible for the subject. While in the clinic, the site should attempt to obtain 2 PK samples, separated by 1-2 hours, if possible. Hours since the last dose of the study medication must be recorded in the eCRF upon collection of the PK sample(s).

[figure not shown]

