## 6.2 Justification for Study Design, Dose, and Endpoints

### 6.2.1 Study Design

This is a multicenter, randomized, double-blind, placebo-controlled, parallel-group, dose-escalation study with an open-label part to examine the safety, tolerability, PK and PD, and preliminary efficacy of TAK-935 as adjunctive therapy in the treatment of subjects with a diagnosis of developmental and/or epileptic encephalopathies demonstrating bilateral motor seizures (ie, drop seizures, tonic-clonic, tonic, bilateral clonic, atonic, myoclonic-atonic, myoclonic-tonic-clonic, focal seizures with bilateral hyperkinetic motor features) (average of  $\geq 2$  per month during the past 3 months) based on the investigator's assessment.

The safety, tolerability, PK, and CCI of TAK-935 after multiple-dose administration either orally or via G-Tube/PEG tube is first assessed (in Part 1), and then the longer-term safety, tolerability, and PK/PD of TAK-935 is assessed (in Part 2), with a seamless transition between Parts 1 and 2. The main goal of this study is to identify the safe and tolerable dose of TAK-935 to assess the efficacy of TAK-935 in subjects with developmental and/or epileptic encephalopathies.

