### **13.3 Determination of Sample Size**

Approximately 20 adult subjects are planned to be randomized. A formal sample size calculation was not performed for this study. The current sample size is deemed appropriate to evaluate the safety and tolerability of TAK-935 before dosing in pediatric subjects <18 years of age. Subjects who fail to complete Part 1 may be replaced and will receive the same treatment as the replaced subject.

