**Footnotes for Appendix A**

(a) The 4-week baseline seizure diary recording can begin as soon as the ICF has been signed. Randomization can occur once the 4-week baseline seizure count of  $\geq 1$  has been obtained and the subject meets all of the inclusion and none of the exclusion criteria.

(b) Three days after each dose up-titration or de-escalation, subjects will be contacted by phone to monitor study drug compliance, concomitant medication use, and AEs.

(c) Subjects who do not enter Part 2 or withdraw early from the study should complete all procedures scheduled for the Final Visit (Visit 7) at time of withdrawal, including dose de-escalation as appropriate, followed by the Follow-up Period (Visits 8 and 9). See Section 6.1 for details.

(d) Dose de-escalation, as appropriate, begins at the Final Visit (ie, if at TAK-935 300 mg BID level, reduce to 200 mg BID for 3 days followed by 100 mg BID for 3 days; if at the 200 mg BID level, reduce to 100 mg BID for 3 days; if at the 100 mg BID level, there is no de-escalation). See Section 6.1 for details.

(e) If urine cannot be collected, the reason should be documented in the source document.

(f) Subjects who are positive for hepatitis C Ab should return to the clinic for an unscheduled visit to provide a blood sample for HCV qPCR.

(g) If the subject is unable to comply with the C-SSRS due to developmental status, a parent proxy may be used for the completion of the C-SSRS. The investigator may also use clinical judgment to assess for suicidal ideation and behavior.

(h) For female subjects only at the Screening and Final Visits.

(i) For female subjects of childbearing potential, a serum pregnancy (hCG) test will be performed at the Screening and Final Visits and a urine pregnancy test will be performed before the morning dose on Day 1 in Part 1 (Visit 2). If urine cannot be collected, the reason should be documented in the source document and the serum pregnancy test obtained at Visit 1 must be confirmed to be negative by the investigator prior to randomization. Additional pregnancy tests may be performed throughout the study at the investigator's discretion.

(j) PE must be captured in the source document. Any clinically significant abnormalities noted prior to administration of study drug should be described and captured on the Medical History form. Any clinically significant changes in PE noted after administration of study drug should be captured on the AE page of the eCRF.

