## 5.0 ANALYSIS ENDPOINTS

### 5.1 Primary Endpoint

Percentage of subjects with at least 1 treatment-emergent adverse event (TEAE), as reported by the subjects or subjects' caregivers or observed by the investigator, after TAK-935 treatment.

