When calculating the frequency and percentage of subjects who reported TEAEs, a subject will be counted only once for each SOC or PT when multiple TEAEs are coded to the same SOC or PT. For the intensity or relatedness summaries, if a subject reports multiple TEAEs coded to the same SOC or PT, the TEAE with maximum intensity or strongest relationship will be included in the summary.

AEs with missing severity will be listed as such in the AE listings, however, will be summarized as severe in summary tables. Similarly, if the relationship of an event is missing, the event will be considered as related but in listings it will be presented as missing.

In general, AEs will be tabulated at the following levels: overall summary (subjects with at least 1 AE in any dose or treatment), the MedDRA SOC, and the MedDRA PT. The tables will include the number and percentage (N[%]) of subjects. The following summary tables will be generated for each study part (Part 1 and Part 2):

- Overview of Treatment-Emergent Adverse Events
- Treatment-Emergent Adverse Events by System Organ Class and Preferred Term
- Treatment-Emergent Adverse Events by Preferred Term
- Serious Treatment-Emergent Adverse Events by System Organ Class and Preferred Term
- Most Frequent (>5% or N>2) Non-Serious Adverse Events by Preferred Term
- Most Frequent (>5% or N>2) Non-Serious Adverse Events by System Organ Class and Preferred Term
- Relationship of Treatment-Emergent Adverse Events to Study Drug by System Organ Class and Preferred Term

- Drug-Related Treatment-Emergent Adverse Events by System Organ Class and Preferred Term
- Drug-Related Treatment-Emergent Adverse Events by Preferred Term
- Severity of Treatment-Emergent Adverse Events by System Organ Class and Preferred Term
- Pretreatment Adverse Events by System Organ Class and Preferred Term

In addition, subject mappings for the TEAEs by SOC and PT will be generated.

Data listings will be provided for PTEs, TEAEs, TEAEs leading to study drug discontinuation, SAEs, and AEs that resulted in death.

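### The per-part TEAE percentages come from overlapping windows of 59 and up to 89 days, with no measure of time at risk

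*Protocol*

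**What the plan says.** The primary endpoint in SAP 5.1 is the "Percentage of subjects with at least 1 treatment-emergent adverse event (TEAE" after TAK-935 treatment. Protocol 13.1.3.1 applies it by part ("TEAEs will be a primary endpoint for each part of the study"), keeps it descriptive ("No statistical testing will be performed or inferential statistics will be generated") and leaves the TEAE definition to the SAP.

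SAP 7.11.1 uses one closing rule for both parts: an event counts if its onset date minus the date of that part's last dose, plus 1, is at most 30. The Part 1 definition says nothing about a first Part 2 dose. The SAP then states "The following summary tables will be generated for each study part (Part 1 and Part 2") and lists tables of numbers and percentages of subjects. SAP 7.11 shows Part 1 by placebo, TAK-935 and overall, Part 2 by treatment received in Part 1, and the two parts combined. SAP 7.7 derives days of exposure for each part, but no listed AE table uses them.

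On contact, Protocol Appendix A schedules AE assessment on Days 1, 11, 21, 31, 41, 85, 91 and 121. Footnote (b) adds calls tied to dose changes: "Three days after each dose up-titration or de-escalation, subjects will be contacted by phone to monitor study drug compliance, concomitant medication use, and AEs".

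**The concern.** Protocol 6.2.1 describes Part 1 as the first assessment and says that "the longer-term safety, tolerability, and PK/PD of TAK-935 is assessed (in Part 2"). A reader will therefore set the two percentages beside each other to judge whether tolerability worsens or settles with longer treatment. A crude percentage of subjects with at least one event rises with the length of observation even when the drug's effect is unchanged. If the windows differ in length, and some days belong to both, that reading is unsafe.

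The overlap also touches the only randomised contrast in the study. A subject randomised to placebo who continues takes open-label TAK-935 from Day 31, yet an event in the following weeks still meets the Part 1 definition.

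**Working it through.** **Inputs.** Part 1 dosing runs Days 1-30. Part 2 dosing starts on Day 31. For subjects on 300 mg BID the taper ends "subsequently to 100 mg BID for 3 days (Days 88-90"), so the last dose is Day 90 (Protocol 6.1). The closing rule is in SAP 7.11.1.

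**The plan's own durations.** Part 1: 20 + 10 = 30 days. Part 2: 10 + 44 + 6 = 60 days. Both agree with the study summary (30 and about 60 days).

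**TEAE windows.** Onset − last dose + 1 ≤ 30 means onset ≤ last dose + 29.

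- Part 1, continuing subject: 30 + 29 = Day 59, so Days 1-59, 59 days.
- Part 1, not continuing, with taper to Day 36 counted as Part 1 dosing (an assumption): Days 1-65, 65 days.
- Part 2, last dose Day 90 (300 mg): 90 + 29 = Day 119, so Days 31-119, 89 days.
- Part 2, last dose Day 87 (200 mg): 86 days. Last dose Day 84 or 85 (100 mg): 83 or 84 days.
- Overlap for continuing subjects: Days 31-59, 59 − 31 + 1 = 29 days.
- Ratio of windows: 89/59 = 1.5.

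**Effect of length alone.** The documents give no expected TEAE risk, so the 30-day risk p is assumed. With a constant hazard, the risk over d days is 1 − (1 − p)^(d/30).

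| Assumed 30-day risk | Part 1 as written, 59 d | Part 2, 89 d | 89 d minus 59 d | 89 d minus 30 d |
|---|---|---|---|---|
| 20% | 35.5% | 48.4% | 12.9 | 28.4 |
| 30% | 50.4% | 65.3% | 14.9 | 35.3 |
| 40% | 63.4% | 78.0% | 14.6 | 38.0 |
| 50% | 74.4% | 87.2% | 12.8 | 37.2 |
| 70% | 90.6% | 97.2% | 6.6 | 27.2 |

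For risks of 30% to 50% the gap is about 13 to 15 points with the windows as written. The last column applies only if Part 1 closes at Day 30.

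**Effect of the overlap.** With four placebo subjects, one who is event-free to Day 30 and has a first event on Days 31-59 moves the Part 1 placebo percentage by 1/4 = 25 points.

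**Scheduled contact.** Part 1 contacts on Days 1, 11, 14, 21, 24 and 31 give gaps of 10, 3, 7, 3 and 7 days. In Part 2, contacts on Days 31, 34, 41, 44, 85, 88, 91 and 121 give gaps of 3, 7, 3, 41, 3, 3 and 30 days. The 41-day gap becomes 37 to 45 days with the ±2-day visit windows. It is 85 − 41 = 44 days for a subject whose dose does not change on Day 41, because no Day 44 call is then triggered. Days 45-59, 15 of the 59 days in Part 1's window as written, lie inside the same gap.

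**The case against.** The strongest reply is that the endpoint is descriptive, "A formal sample size calculation was not performed for this study", and no test between parts is planned. AEs are summarised part by part, exposure is summarised separately, and dose dates and TEAEs are listed by subject, so a careful reader could rebuild the rates. This stands to the extent that no error rate is affected and the harm is one of interpretation. It does not remove the point, because description is the study's only primary output and the double counting is in the definition itself.

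A second reply is that equal windows would not make the parts comparable. The first 30 days of Part 1 are planned as 10 days each at 100, 200 and 300 mg BID. The first 30 days of Part 2 are planned as 10 days at 200 mg and 20 at 300 mg, unblinded and mostly after prior exposure. This is correct and should be stated beside any such figure.

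Two stronger readings are tempting.

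- **A threefold imbalance, 30 against 89 days.** A reader might infer this from the 30 dosing days of Part 1. It adds the post-dose tail to Part 2 and leaves it off Part 1, whereas SAP 7.11.1 gives the tail to both. The partial-date rule in SAP 7.1.3.1 treats continuing and non-continuing subjects differently and so hints at a cut at the first Part 2 dose. The TEAE definition does not state one.
- **The long gap means that Part 2 under-reports.** The gap in scheduled contact is real. However, Protocol 10.2.1.2 suggests asking about the time since the last visit and accepts reports at any time. It also requires follow-up of possible AEs seen in the diary. Lower ascertainment is possible but not shown.

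**Conclusion.** The concern holds. As written, the Part 1 and Part 2 TEAE percentages rest on windows of 59 and up to 89 days that share 29 days, and the readable text plans no time-at-risk measure. Length alone accounts for about 13 to 15 points between parts at an assumed 30-day risk of 30% to 50%, and about 7 to 13 points at 70% and 20%. It would be 35 to 38 points for risks of 30% to 50% only if Part 1 were cut at the first Part 2 dose. These figures assume a constant hazard, planned visit days and full dosing to Day 90.

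The more direct defect is the overlap, because it can place open-label TAK-935 events in the randomised placebo column. A longer window raises the Part 2 percentage and sparser contact may lower it, so the sign of the net distortion cannot be stated. The consequence is for interpretation, not for any test. The change is worth making because it is cheap and concerns the primary endpoint.

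**What to change.** 1. In SAP 7.11.1, end the Part 1 TEAE window at the first Part 2 dose for continuing subjects. Keep the 30-day tail for those who do not continue. Align the date rules in SAP 7.1.3.1 with this.
2. Beside n (%), report two descriptive figures for each part: first-event incidence per person-time over these non-overlapping windows, and the percentage of subjects with a TEAE in the first 30 days of the part. Add a note that dose sequence, blinding and prior exposure still differ between parts.

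The two changes belong together. Step 1 alone would leave continuing subjects with 30 days in Part 1 against up to 89 in Part 2 (89/30 = 3.0), which makes the crude percentages less comparable. Both use data already collected, keep the rule against inferential statistics and need no protocol amendment. The cost is a few extra columns, which will be imprecise with about 20 subjects.

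Optional: one AE phone contact between Days 44 and 85. This changes the schedule in Appendix A and so needs a protocol amendment. A call on Day 65 would split the gap into 21 and 20 days, which is still longer than any scheduled gap on Days 1-31.
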